5.0 STUDY DRUG

5.1 Formulation, Packaging and Storage

All investigational medication to be used in this study [supplied by American Regent, Inc.] will have been prepared according to Good Manufacturing Practices (GMP).

FCM (trade name, Injectafer®) will be supplied as 15 ml vials, containing 750 mg of iron as 5% w/v iron containing a polynuclear iron(III)-hydroxide 4(R)-(poly-(1-->4)-O α -D-glucopyranosyl)-oxy-2 (R), 3(S), 5(R), 6-tetrahydroxy-hexonate complex in a solution of water for injection [50 mg/ml] and will be labeled according to FDA investigational regulatory requirements.

Placebo (normal saline) will be supplied as 15 ml fill in 20 ml vials.

All IV study drugs (FCM and Normal Saline) must be kept in a secure place at the investigational site, and stored at room temperature (see USP). The study medication should not be frozen. Vials may not be used for more than 1 dose, or for more than 1 participant. All vials (used and unused) should be kept by the study staff for reconciliation by the monitor unless the site is unable to retain them and documentation (site or institution process or procedures, or SOPs, for example) is present. Following reconciliation, sites may destroy used and unused study drug on site using local procedures, provided a drug destruction policy is in place, or it may be returned to American Regent, Inc.

5.2 Drug Administration/Regimen

The Principal Investigator or designee will supervise administration of the study drug to participants. The participants should remain blinded to the identity of the study drug for the duration of the trial.

Group A: Group A (FCM) will receive a 750 mg undiluted blinded dose of IV FCM at the rate of approximately 100 mg (2 mL)/minute (approximately 7 minutes 30 seconds) on Day 0 and Day 7, not to exceed an individual dose of 750 mg or a cumulative dose of 1500 mg per treatment cycle.

Group B: Group B (placebo) will receive a blinded placebo (15 cc of normal saline) IV push at 2 mL/minute (approximately 7 minutes 30 seconds) on Day 0 and Day 7.

Note: To avoid unblinding on the dose administration worksheet, if a participant is under 50 kg (110 pounds), the volume of FCM or placebo administered should be calculated based on the participant's weight, e.g. a 45 kg participant will receive a 13.5 mL dose of FCM or placebo.

All participants will be dosed every 6 months. At each 6-month interval, 2 doses of study drug will be administered as described above for Day 0 and Day 7. The same randomized treatment will be administered if Hgb <13.5 g/dL (females) or <15.0 g/dL (males) and serum ferritin <100 ng/mL or 100 to 300 ng/mL with TSAT <20%; placebo will be administered to participants in the FCM group who do not meet the above criteria.

Site personnel will ensure the participant and blinded study staff are not able to observe the preparation or administration of study treatment injections.

5.3 IV Medication Precautions

When administering FCM or Placebo, the following precautions will be taken:

- The participant will be evaluated clinically prior to drug administration to assess the development of clinically significant conditions.
- The vials will be visually inspected for particulate matter and discoloration before use. If noted, the vial will not be used, and the Investigator or his designee will notify the sponsor or sponsor's designee for replacement of the study drug, and for direction on the return of the unused vial.
- Heart rate and blood pressure will be assessed pre-, immediately post, and 30 minutes post administration. Participants will be discharged from the site by the Investigator or his or her designee only if there are no significant signs or symptoms 30 minutes after the administration is completed.
- The participant will be monitored for at least 30 minutes for serious acute reactions as hypersensitivity or bioactive (labile) iron reactions to non-dextran IV iron products have rarely been reported. The reactions include: hypotension, loss of consciousness, bronchospasm with dyspnea, shortness of breath, and seizures.
 - In the event a serious acute reaction is seen, the site must have the capability to provide appropriate resuscitation measures. These may include IV NS, IV epinephrine, steroids, and/or antihistamines.

5.4 Drug Accountability

Investigators will keep records of the receipt, administration and return of the study drug (FCM). They will not allow the study drug to be used for purposes other than as directed by this protocol. The investigator agrees that he/she will not supply study medication to any persons other than those randomized in the study, or to investigators not listed on the FDA 1572. When the study is completed, or if it is prematurely terminated, a final inventory of all clinical supplies must be compiled and the remainder of the unused study drug will be returned to American Regent, Inc., or destroyed on site, per the site's documented locally accepted policies. All data regarding the study drug must be recorded as per the Monitoring Plan.

5.5 Concomitant Medication

All Concomitant medications will be recorded in the eCase Report Form (eCRF).

Note: Oral iron supplementation is permitted prior to screening and during the course of the study.

No prophylactic medications specifically for administration of study drug may be administered prior to study drug administration without prior approval from American Regent, Inc. Other standard therapies are permitted.

5.6 Blinding

All participants and blinded study staff will be blinded to the content of study drug for the duration of the trial.

During the period of study drug administration, the blinded personnel will not be with the subject or in a location that could result in the blind being inadvertently broken. However, the Principal Investigator or designee will be available in the event of an emergency, and/or the need for adverse event assessment. All blinded study personnel will be blinded to the post-treatment iron indices and serum phosphorous laboratory results, as the values may break the blind.

The blinding will be maintained until the study is complete, and the database has been locked. In the event of an emergency that would require the investigator to be aware of the treatment allocation prior to database lock, the investigator can obtain this information, on a per participant basis. **It is recommended to contact the sponsor's Medical Monitor or designee prior to unblinding.** If a participant's treatment assignment is unblinded, the sponsor must be contacted immediately via telephone.

6.0 STUDY PROCEDURES

6.1 Informed Consent

Prior to any study specific procedures, the investigator or his or her designee must explain to each participant the nature of the study, its purpose, procedures to be performed, expected duration, and the benefits and risks of study participation. After this explanation the participant must voluntarily sign an informed consent statement (Required Elements of Informed Consent, 21 CFR 50.25). The participant will be given a copy of the signed consent form.

6.2 Screening Phase (Day -28 to Day 0)

6.2.1 Screening Visit

Each participant who has signed the informed consent and qualifies for inclusion will undergo the following clinical evaluations to confirm eligibility for the study (all procedures to be performed by blinded study personnel):

- Demographic and medical history including NYHA heart failure class and prior heart failure hospitalizations

- Left ventricular ejection fraction (historical values may be used if performed within 24 months of the screening visit, or 36 months if LVEF \leq 30%) must be performed at least 12 weeks after major cardiac intervention-including CABG, valvular intervention, or cardiac resynchronization therapy device implantation
- Blood samples for hematology, iron indices, and NT-proBNP (central laboratory)
- Concomitant medications
- Review inclusion/exclusion criteria
- Enter participant in the Interactive Response Technology (IRT) system to obtain screening number.

Participants who do not meet study entry criteria should be entered into the IRT system as a screen failure.

6.3 Treatment Phase (Day 0 to Day 7)

6.3.1 Day 0 Visit

All eligible participants will be randomized to either Group A or Group B in a 1:1 ratio based on a pre-determined randomization schedule via an IRT system.

The following will be obtained and/or completed before contacting IRT for randomization:

For all participants (all procedures to be performed by blinded study personnel):

- Verify all inclusion and exclusion criteria
- Height and weight
- Targeted physical exam
- Blood samples for central lab hematology, chemistries and iron indices for all participants; For Hypophosphatemia Sub-Study participants only: 1,25 (OH)₂ Vitamin D, 25 (OH) Vitamin D and PTH.
- Review concomitant medications
- Urine or serum pregnancy test (women of childbearing potential only)
- Administer 6MWT per standardized procedure

The IRT system will then be contacted by an **Unblinded** study team member and all eligible participants will be randomized to either Group A or Group B in a 1:1 ratio with stratification by region based on a pre-determined randomization schedule. After assignment of the treatment group the following will occur:

Note: To avoid unblinding on the dose administration worksheet, if a participant is under 50 kg, the volume of FCM or placebo administered should be calculated based on the participant's weight, e.g. a 45 kg participant will receive a 13.5 mL dose of FCM or placebo.

Note: All IV injection start and stop times should be captured in hh:mm:ss format.

Group A:

- Verify amount of single FCM dose (15 mg/kg up to a maximum dose of 750 mg) (unblinded staff)

- Pre-administration, obtain heart rate, blood pressure, and body temperature (blinded staff)
- Administer FCM as a slow IV injection at the rate of approximately 2 mL /minute taking appropriate measures to ensure the participant and all blinded staff members remain blinded to the treatment being administered (unblinded staff).
- Document start and stop time of FCM administration and the total dose and volume administered (unblinded staff)
- Post-administration, obtain heart rate and blood pressure immediately after and 30 minutes after FCM administration (blinded staff). Participants will be discharged from the site by the Investigator or his or her designee only if there are no significant signs or symptoms 30 minutes after the administration is completed.
- Adverse event / serious adverse event assessment (starting at beginning of FCM injection) (blinded staff)

Group B:

- Pre-administration, obtain heart rate, blood pressure, and body temperature (blinded staff)
- Administer a 15 mL dose of placebo (normal saline) as a slow IV injection at the rate of approximately 2 mL /minute taking appropriate measures to ensure the participant and all blinded staff members remain blinded to the treatment being administered (unblinded staff).
 - Document start and stop time of placebo administration and the total volume administered (unblinded staff).
 - Post-administration, obtain heart rate and blood pressure immediately after and 30 minutes after placebo administration (blinded staff). Participants will be discharged from the site by the Investigator or his or her designee only if there are no significant signs or symptoms 30 minutes after the administration is completed.
 - Adverse event and serious adverse event assessment (starting at beginning of placebo injection) (blinded staff).

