3.0 OVERALL STUDY DESIGN AND RATIONALE

3.1 Overall Study Design

This is a double-blind, multicenter, prospective, randomized, placebo-controlled study to assess the effects of IV FCM compared to placebo on the 12-month rate of death and hospitalization for worsening heart failure, and change in 6MWT at 6 month for patients in heart failure with reduced ejection fraction and with iron deficiency.

After an initial screening period of up to 28 days, eligible participants will be stratified by region and randomized in a 1:1 ratio to FCM or placebo. Study drug administration will occur on Day 0 and Day 7 as an undiluted slow IV push, with additional study visits (in

person or via telephone) planned at 3 month intervals, and additional dosing administered every 6 months as applicable (based on dose regimen below). For all participants, hematology, ferritin and transferrin saturation (TSAT), with appropriate safety evaluations, to determine additional treatment, will occur at 6 month intervals.

In a subset of sites, a sub-study will be conducted to characterize serum phosphate levels overtime in participants in heart failure with iron deficiency after dosing with FCM (see Appendix 1).

Initial treatment will occur on Day 0 and Day 7. On Day 0 and 7, Group A (FCM) will receive a 750 mg undiluted, blinded dose of IV FCM at the rate of approximately 100 mg (2 mL)/minute; Group B (placebo) will receive a blinded placebo (15 cc of normal saline) IV push at 2 mL/minute. Participants in Group A with body weight <50 kg (110 pounds) will have individual FCM doses adjusted to 15 mg/kg, not to exceed an individual dose of 750 mgs or a cumulative dose of 1500 mg per treatment cycle. Placebo dosing will be adjusted for weight based on volume.

All participants randomized will be dosed every 6 months. Participants randomized to the FCM arm will be dosed as indicated based on hemoglobin levels (i.e. Hgb <13.5 g/dL [females] or <15.0 g/dL [males]) and iron studies (i.e. serum ferritin <100 ng/mL or 100 to 300 ng/mL with TSAT <20%). Participants not meeting pre-specified laboratory criteria for blood counts and iron studies and all participants randomized to the placebo arm will be administered IV placebo infusion at each visit.

Unblinded site personnel, responsible for preparation and administration of the FCM or Placebo, will ensure that the participant and all blinded site staff are not able to observe the preparation or administration of study treatment.

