4.3 Participant Assignment and Randomization Process

Participants who meet all inclusion requirements and no exclusionary criteria will be offered enrollment in this study. Enrolled participants will be stratified by region and randomized in a 1:1 ratio to receive either IV FCM or IV Placebo.

The FCM Group will initially receive 2 blinded doses of FCM at 15 mg/kg to a maximum of 750 mg per dose for a maximum total dose of 1500 mg.

The Placebo Group will receive 2 blinded doses of 15 mL of normal saline.

Participants and blinded study staff will remain blinded to the treatment assignment for the duration of the study.

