6.4.3 Additional Study Drug Dosing (Every 6 Months)

All participants will be dosed every 6 months. At each 6-month interval, a course of 2 doses of study drug will be administered as described above for Day 0 and Day 7 (Section 6.3). For group A, FCM will be administered if Hgb < 13.5 g/dL (females) or <15.0 g/dL (males) and serum ferritin <100 ng/mL or 100 to 300 ng/mL with TSAT <20%; observe carefully that placebo (normal saline) will be administered to participants in the FCM group who do not meet the above criteria. All group B participants will receive placebo (normal saline).

6.4.3.1 6 Month Dosing Visit #1 (Days 180 ± 7 , 360 ± 7 , 540 ± 7 , 720 ± 7 , 900 ± 7 , 1,080 ± 7 ...EOS)

On the first of the 2 dosing visits, the following will be performed by blinded study staff for all participants:

- Weight
- Urine or serum pregnancy test (women of childbearing potential only)
- Adverse event / serious adverse event assessment, including evaluation of potential endpoint events (see Section 10.2).
- Review concomitant medications
- Administer 6MWT per standardized procedure (at the 6 and 12 month visits).

Note: To avoid unblinding on the dose administration worksheet, if a participant is under 50 kg, the volume of FCM or placebo administered should be calculated based on the participant's weight, e.g. a 45 kg participant will receive a 13.5 mL dose of FCM or placebo.

For Group A participants the following will be performed:

- Verify if participant will receive FCM or placebo, based on the following criteria from recent labs (within 20 days). Participants will receive FCM if the Hgb <13.5 g/dL (females) or <15.0 g/dL (males) and serum ferritin <100 ng/mL or 100 to 300 ng/mL with TSAT <20%. If the participant does not meet these criteria, placebo (normal saline) will be administered. (unblinded staff)
- As appropriate based on criteria above, verify amount of single FCM dose (15 mg/kg up to a maximum dose of 750 mg) or placebo (15 mL). (unblinded staff)
- Pre-administration, obtain heart rate, blood pressure, and body temperature. (blinded staff)
- Administer FCM or placebo as a slow IV injection at the rate of approximately 2 mL /minute. Appropriate measures must be taken to ensure the participant and all blinded

staff members remain blinded to the treatment being administered (unblinded staff)

- Document start and stop time of IV administration, and the total dose and volume administered (unblinded staff)

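### For participants under 50 kg, protocol version 3 gives two conflicting placebo volumes; following the 15 mL step literally would undo the protocol's own safeguard against unblinding

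*Combined protocol and SAP*

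**What the plan says.** All references are to the final protocol (version 3) unless stated.

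**Fixed 15 mL, no weight condition**
- Section 4.3: "The Placebo Group will receive 2 blinded doses of 15 mL of normal saline".
- Group B step in 6.3.1: "Administer a 15 mL dose of placebo (normal saline) as a slow IV injection". The Group B steps in 6.3.2, 6.4.3.1 and 6.4.3.2 repeat it.
- Group A step at repeat dosing (6.4.3.1, repeated in 6.4.3.2), where an FCM-arm participant may receive saline: "verify amount of single FCM dose (15 mg/kg up to a maximum dose of 750 mg) or placebo (15 mL".
- The synopsis gives placebo as 15 cc and applies the weight adjustment to Group A only.

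**Weight-based volume**
- Section 3.1: "Placebo dosing will be adjusted for weight based on volume". SAP v1.3 section 1.2 says the same.
- Section 5.2: "To avoid unblinding on the dose administration worksheet, if a participant is under 50 kg (110 pounds), the volume of FCM or placebo administered" is to be worked out from body weight.
- The Notes in 6.3.1, 6.3.2, 6.4.3.1 and 6.4.3.2 repeat this, with a worked example: "a 45 kg participant will receive a 13.5 mL dose of FCM or placebo".

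The Group A step in 6.3.1 carries the weight rule within the step itself: "Verify amount of single FCM dose (15 mg/kg up to a maximum dose of 750 mg) (unblinded staff". The Group B step has no counterpart.

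**The concern.** Below 50 kg the FCM volume falls with weight. If the placebo volume stays at 15 mL, the volume on the record separates the two products. The Notes were written to prevent this, so the sponsor already treats recorded volume as a route to unblinding. The steps that staff carry out were not brought into line, and two staff members who each follow a printed instruction can give different placebo volumes at the same weight.

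What is at stake is the blind in a low-weight subgroup. Blinded staff weigh the participant, so they can work out what volume the weight rule implies. They take vital signs before and straight after the injection, so its duration may be noticed. On Day 0, start and stop times are recorded to the second. Blinded staff also run the follow-up 6MWT, which is effort-dependent and the third tier of the primary endpoint, and they collect potential endpoint events.

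**Working it through.** **Inputs.** FCM dose rule: 15 mg/kg up to 750 mg (Group A step, 6.3.1). Concentration: 750 mg in a 15 mL vial, so 750 / 15 = 50 mg/mL (5.1). Injection rate: about 2 mL/min for both products (5.2). Placebo volume: 15 mL under the Group B step, or equal to the FCM volume at that weight under the Note.

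**Formulas.** FCM volume = min(15 × weight, 750) / 50 mL. Injection time = volume / 2 minutes.

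**The plan's own figure.** At 45 kg: 45 × 15 = 675 mg, and 675 / 50 = 13.5 mL. This reproduces the Note's example exactly.

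**Comparison if the Group B step is followed literally** (placebo 15 mL, 15 / 2 = 7.5 min, or 7:30, at every weight):

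| Weight | FCM dose | FCM volume | FCM time | Volume gap | Time gap |
|---|---|---|---|---|---|
| 35 kg | 525 mg | 10.5 mL | 5:15 | 4.5 mL | 135 s |
| 40 kg | 600 mg | 12.0 mL | 6:00 | 3.0 mL | 90 s |
| 45 kg | 675 mg | 13.5 mL | 6:45 | 1.5 mL | 45 s |
| 49 kg | 735 mg | 14.7 mL | 7:21 | 0.3 mL | 9 s |
| 50 kg or more | 750 mg | 15.0 mL | 7:30 | 0 | 0 |

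**If the Note is followed**, both products have the same volume and time at any weight, and the record says nothing about the arm.

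**Day 0 and Day 7.** Every Group A participant receives FCM and every Group B participant receives saline. Under the weight rule, FCM below 50 kg is always less than 15 mL, so a recorded 15 mL at such a weight points to placebo. A smaller volume points to FCM only where staff are known to follow the step rather than the Note.

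**Repeat cycles.** Group A participants who no longer meet the laboratory criteria also receive saline. A recorded 15 mL then shows saline but not necessarily the placebo arm. Where the step is followed, a volume below 15 mL would still point to FCM, and so to the FCM arm.

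**The case against.** The best reply is that the Note governs. It stands ahead of the Group A and Group B steps at every dosing visit, names its trigger, covers both products, states its purpose and works an example. Section 3.1 and the SAP agree with it. Section 5.2 treats FCM the same way, with a flat 750 mg followed by the Note, so the whole can be read as a general rule with an exception below 50 kg.

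There are further safeguards. Unblinded staff record volume and times, and section 5.6 keeps blinded staff away from the administration. The baseline 6MWT precedes randomization. Heart failure hospitalizations are adjudicated by a committee blinded to treatment (10.2). The worksheet is not among the documents and may already apply the weight rule.

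Most of this stands as a limit on the consequence. It does not remove the conflict. Nothing in the protocol says that the Note overrides the step, and section 4.3 has no Note beside it. The Group A steps build in the weight rule while the Group B steps do not, which invites a literal reading of 15 mL. The Note's stated purpose also assumes that the worksheet could unblind someone.

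A reader might infer that the volume reveals the arm with certainty for every participant under 50 kg at every visit. The documents do not support that. It requires staff to set the Note aside and a blinded person to see the record or the timing and link it to weight. It fails for 15 mL in repeat cycles. Near 50 kg the difference is trivial: 9 seconds at 49 kg, at a rate that is itself only approximate.

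**Conclusion.** The contradiction is real and sits in the current text. For participants under 50 kg, protocol version 3 gives two placebo volumes at every dosing visit, and one of them, followed as written, defeats a safeguard that the protocol states for itself. At 45 kg the gap is 1.5 mL, or about 45 seconds. It is larger at lower weights and nil from 50 kg.

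The consequence is conditional: staff must follow the step rather than the Note, and a blinded person must see the worksheet or the timing and know the weight. The arm itself could be read from 15 mL only at Day 0 and Day 7.

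A reader might also infer a biased primary endpoint. The documents do not show that. Blinded adjudication means that any effect on heart failure hospitalization would have to enter through site decisions to admit or report. Any effect on the 6MWT would need blinded staff to have worked out the arm. The number of participants under 50 kg is not given, so no count is offered; for scale only, each 1% of the planned 3014 is about 30 participants (0.01 × 3014 = 30.1). Sample size, power and alpha are unaffected.

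**What to change.** Reconcile section 4.3, the Group B steps in 6.3.1, 6.3.2, 6.4.3.1 and 6.4.3.2, the Group A repeat-dosing steps in 6.4.3.1 and 6.4.3.2, and the synopsis with sections 3.1 and 5.2 and the Notes. Each dosing visit should carry one unambiguous volume instruction that meets the stated blinding purpose, including for saline given to Group A participants. Check that the dose worksheet and SAP section 1.2 agree with the result. Which volume applies is for the sponsor to decide.

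The cost is protocol wording and a memo to sites. No new procedure, visit or analysis is needed.
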